Background and Rationale	
The kidneys play a central role in maintaining systemic homeostasis through regulation of electrolyte balance, fluid distribution, and removal of metabolic waste. Despite their functional reserve, renal physiology undergoes gradual decline with advancing age, even in the absence of overt kidney disease. These structural changes are accompanied by progressive nephron loss, reduced renal perfusion, and impaired oxygenation, ultimately contributing to diminished filtration capacity.
 
Traditional clinical markers of kidney function, such as serum creatinine and estimated glomerular filtration rate (eGFR), do not fully capture these early microstructural and physiological changes. Both are indirect measures influenced by multiple confounding factors and often remain within normal limits until significant nephron loss has occurred. This diagnostic delay presents a major challenge in distinguishing between normal renal aging and early pathological decline. In recent years, multiparametric magnetic resonance imaging (mpMRI) has emerged as a promising non-invasive approach to characterize renal physiology at a tissue level. By integrating different imaging techniques – T1, T2 and T2*-mapping, arterial spin labeling (ASL) and intravoxel incoherent motion mpMRI enables a more comprehensive evaluation of renal function than conventional methods. Standardization efforts have further improved its reproducibility, but the specific impact of physiological aging on renal MRI parameters remains insufficiently explored.
 
The purpose of this study is to investigate age-related changes in renal tissue characteristics using multiparametric MRI in a cohort of healthy individuals and to assess the potential of these imaging biomarkers for differentiating physiological aging from early functional deterioration.

Risk / Benefit Assessment	Magnetic resonance imaging (MRI) is a safe imaging technique without any evidence of detrimental secondary effects. However, it carries a risk for individuals with metal or electronic implants and may cause discomfort, particularly for claustrophobic individuals. This study design does not offer any direct benefits to the participants but may benefit future participants by facilitating earlier detection of renal function impairment and a more customized therapy regimen.
Objective(s)	
This study is a prospective, exploratory, single-center trial aiming on the exploration of the value of mpMRI in the assessment of renal function.
 
The primary null hypothesis proposes no correlation between serum creatinine/eGFR values and MRI parameters, while the alternative hypothesis suggests a significant correlation.
 
 
○ The first sub-aim is to assess kidney function with mpMRI across age groups,
 
○ The second sub-aim is to compare mpMRI parameters between healthy participants and their age-matched metabolic syndrome group, and
 
○ The third sub-aim is to assess intra- and inter-reader variability.
 

Endpoint(s)	
Primary endpoint:
 
 
• 1st aim: Exploration of the value of mpMRI in the assessment of renal function with serum creatinine and eGFR as the gold standard for comparison.
 
 
Secondary endpoints:
 
 
• 1st sub-aim: Comparison across the defined age groups.
 
• 2nd sub-aim: Assessment of intra- and inter-reader variability of MRI parameters.
 

Study Design	Open label, non-randomised study
Statistical Considerations	The study aims to enroll 60 healthy participants, with 20 participants per age group (20-40a, 40-60a and > 65a). Multiple MRI parameters will be used to describe the kidney's functional aspects, and statistical comparisons will be performed using t-tests, ANOVA as well as correlation coefficients and a multivariable ANOVA test. The data will be presented using histograms and box plots. Measures of intra- and inter-reader agreement will be used to assess differences between different readers. All primary analyses will be performed with the full analysis set.

Inclusion- / Exclusion Criteria	
To be eligible for participation, subjects must meet the following inclusion criteria:
 
 
- Informed consent as documented by the signature (Informed Consent Form)
 
- participants <math>\geq 18</math> years of age
 
- participants must refrain from consuming food or beverages for three hours before the MRI
 
 
The presence of any of the following exclusion criteria will lead to exclusion of the participants:
 
 
o Women who are pregnant or breast feeding
 
o Intention to become pregnant during the course of the study and lack of safe contraception
 
o inability to follow the procedures of the study, e.g., due to language problems, psychological disorders, dementia, etc. of the participant.
 
o enrolment of the investigator, his/her family members, and other dependent persons
 
o participants with non-MRI compatible metallic or electronic implants, devices, or metallic foreign bodies (cardiac pacemaker, shrapnel, cochlea implants, neurostimulator, or other non-MRI compatible implants).
 
o history of hypertension
 
o history of renal disease as indicated by a normal Quick-Serum-Creatinine level of less than 105 <math>\mu\text{mol/l}</math>
 

Number of Participants with Rationale	We plan to recruit 60 participants (20 participants of each age group) to allow for a sufficient cohort size for statistical analysis.
Study Intervention	
 
• Capillary blood draw
 
• MRI without contrast agent 20-30 minutes
 

Control Intervention	/
Study procedures	The participants will fast (no food or drinks for 3 hours) and undergo a multiparametric MRI examination prior to a capillary blood draw (if no recent ( $<1$ week) blood sample is available in their medical record). MRI parameters will then be examined by two readers and statistical analysis will be conducted.
Study Center(s)	University of Zurich Hospital
Data privacy	The project data will be handled with utmost discretion and access will only be given to authorized personnel. Participants will be identified by a unique participant number, and MRI scans will be saved using a pseudonymized identifier. The study data will be stored on password-secured computers and servers for a minimum of 10 years after study termination, and periodic sampling and quality control will be performed. The study-related clinical data will be stored on a password-protected share, accessible only to dedicated users within the University Hospital Zurich network, and the key to translating the pseudonymized participant identifier to the real participant's name will be kept at the local study center.
Ethical consideration	This study aims to investigate the efficacy of different MRI techniques for assessing renal function in healthy individuals. The results may provide valuable insights into the diagnosis and treatment of age-related kidney diseases. Participants will be fully informed about the trial's purpose, procedures, potential risks and benefits, and any other relevant details that may affect their decision to participate. Incidental findings will be reported unless participants opt out beforehand.
GCP Statement	This study will be conducted in compliance with the protocol, the current version of the Declaration of Helsinki, the ICH-GCP, the HRA as well as other locally relevant legal and regulatory requirements.

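### The primary creatinine correlation has no sex term in a cohort open to both sexes; a sex-adjusted correlation is a nearly free improvement

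*Combined protocol and SAP*

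**What the plan says.** The Objective(s) section sets the primary hypothesis: "The primary null hypothesis proposes no correlation between serum creatinine/eGFR values and MRI parameters". Endpoint(s) repeats the pairing, describing the assessment of mpMRI "with serum creatinine and eGFR as the gold standard for comparison". Creatinine is therefore a reference in its own right and not only an input to eGFR. The eGFR equation is not named.

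Statistical Considerations gives the methods in one sentence: "statistical comparisons will be performed using t-tests, ANOVA as well as correlation coefficients and a multivariable ANOVA test". No covariate, stratum or partial correlation is attached to the correlation coefficients. The multivariable ANOVA has no stated factors and is not linked to the primary hypothesis. The same section says that primary analyses use the full analysis set, which settles who is analysed but not how.

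On recruitment: "The study aims to enroll 60 healthy participants, with 20 participants per age group". No sex quota is set. Inclusion- / Exclusion Criteria excludes "Women who are pregnant or breast feeding", so other women can enter, and its creatinine threshold of 105 µmol/l is the same for men and women. Background and Rationale says of creatinine and eGFR: "Both are indirect measures influenced by multiple confounding factors". The analysis text does not take this up.

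**The concern.** Suppose women have lower creatinine than men at the same filtration rate because they generate less of it. A correlation computed over both sexes then mixes two things: the within-sex relation, which carries the renal signal, and a between-sex contrast, which does not.

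Three consequences are possible:

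- **Dilution.** The sex gap adds spread to creatinine that no MRI parameter tracks, so a real correlation shrinks. This needs only the creatinine gap.
- **False correlation.** An MRI parameter that differs by sex for other reasons correlates with creatinine without any link to function. This needs a sex difference in the MRI parameter as well.
- **Masking.** If that sex difference runs against the true relation, the two can cancel.

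This is separate from the sex mix across age bands. It arises with exactly 10 men and 10 women in each band. Because the plan examines several MRI parameters, those that differ most by sex could be singled out, or missed, as markers of renal function.

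**Working it through.** **The plan's own figure.** The sample size of 60 cannot be reproduced. Number of Participants with Rationale says only that it is "to allow for a sufficient cohort size for statistical analysis", with no alpha, power or target correlation. For orientation, Fisher's z at an assumed two-sided 5% level gives 80% power at r = tanh[(1.960 + 0.842)/√57] = tanh(0.371) = 0.355.

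**Closed form, exact 30:30 sex split.** Let ρ be the within-sex correlation, and let dc and dm be the male-female differences in creatinine and in the MRI parameter, in within-sex SDs. All are assumed. Then

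r(unadjusted) = (ρ + dc·dm/4) / √[(1 + dc²/4)(1 + dm²/4)].

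- *Dilution* (ρ = 0.355 in size, dm = 0): for dc = 1.5, r = 0.355/√1.5625 = 0.355/1.25 = 0.284. Power is Φ(atanh(0.284)·√57 − 1.96) = Φ(0.244), about 60%. For dc = 0.5, 1 and 2, power is 77%, 70% and 49%.
- *False correlation* (ρ = 0): for dc = 1.5 and dm = 0.5, r = 0.1875/√(1.5625 × 1.0625) = 0.146, and the nominal 5% test rejects about 20% of the time. With dm = 0, rejection stays at 5%.
- *Masking* (ρ = −0.355, dc = 1.5, dm = 0.8): r = (−0.355 + 0.300)/√(1.5625 × 1.16) = −0.055/1.346 = −0.04. Power is about 5% unadjusted and 80% sex-adjusted.

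Simulation with 20,000 replicates per scenario agreed. The sex-adjusted test rejected about 5% of the time in every null scenario.

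**On the creatinine scale.** A large simulated population expresses the gap as a percentage. All of its inputs are assumptions except the age bands and the 105 µmol/l limit:

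- 50:50 sex split; equal age bands, with the oldest capped at 80;
- GFR = 105 − 0.6·(age − 50) + N(0, 12);
- creatinine = 80·105/GFR, with 8% noise and a 0.3% per year fall in generation, lowered in women by the stated gap and kept only if below 105;
- MRI-GFR correlation 0.5.

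| Creatinine gap | Creatinine variance due to sex | r unadjusted | r sex-adjusted | Power unadjusted | Power adjusted | Rejection, no MRI-GFR link, 0.5 SD MRI sex difference |
|---|---|---|---|---|---|---|
| 15% | 21% | −0.32 | about −0.37 | 71% | about 84% | 14% |
| 20% | 34% | −0.29 | about −0.37 | 61–62% | about 84% | 19% |
| 25% | 47% | −0.26 | about −0.37 | 52% | about 84% | 24% |

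At a 5% gap the difference nearly vanishes: power is about 81% unadjusted against 82% adjusted, and false rejection is about 6%. If the MRI sex difference is only 0.2 SD, false rejection over the 5 to 25% range is 5 to 8%.

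**Cost of adjusting.** With no sex gap at all, power at ρ = 0.355 is 79.3% adjusted against 80.0% unadjusted.

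**The case against.** The strongest reply is that the plan never says the sexes will be pooled. A reader might infer that an unadjusted analysis over men and women has been chosen. The documents do not support that: they are silent on sex, and the multivariable ANOVA could include it. This objection stands as to certainty. It does not remove the point, because a correlation coefficient with no covariate or stratum is by default the unadjusted one, and the ANOVA is not tied to the primary hypothesis.

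Second, creatinine is only half of a jointly named reference. A reader might infer that the whole primary hypothesis is compromised, or that the slash in Objective(s) treats the two markers as interchangeable. Neither follows. Endpoint(s) joins them with an ordinary conjunction, and an eGFR equation that contains sex would already carry a correction. What remains is that no equation is named and nothing says which marker decides, so a creatinine result could stand as the primary finding.

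Third, every magnitude is assumed, and a small gap does little harm. That is correct, and it is why ranges are shown.

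Fourth, the study calls itself exploratory and states no power target, so no promised power is missed. That lowers the stakes. Even so, the plan states a null and an alternative hypothesis, and exploratory status does not remove a bias.

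**Conclusion.** The point holds for the creatinine part of the primary analysis, as a cheap improvement. The listed method is a plain correlation, both sexes can enrol, and a sex-adjusted correlation is better at almost no cost.

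Dilution rests on one assumption, a lower creatinine in women at equal filtration. False or masked correlations also need an MRI parameter that differs by sex, and no section says that any does. It would go too far to conclude that a significant creatinine correlation in this trial must be an artefact of sex: with no MRI sex difference, the unadjusted test keeps its 5% level.

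Under the stated assumptions, the unadjusted analysis ranges from practically no loss at a 5% gap to about 32 points of power at 25% (84 − 52). These are illustrations, not estimates for this cohort.

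**What to change.** In Statistical Considerations:

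1. Specify the creatinine part of the primary analysis as a sex-adjusted partial correlation, with creatinine on one prespecified scale (for example, log). The scale must be fixed because a partial correlation on raw creatinine and a regression on log creatinine plus sex are not strictly the same analysis.
2. Show the scatter plots of each MRI parameter against creatinine by sex.
3. Name the eGFR equation, so that a reader can see whether it contains sex.
4. Report any unadjusted creatinine correlation only as descriptive.

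The cost is a few sentences, sex recorded for each participant, and one degree of freedom out of 58: under one point of power if there is no sex gap. Recruitment and sample size do not change. The adjustment does not deal with the shared dependence of MRI parameters and creatinine on age in a cohort recruited by age band, which is a separate matter.

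### Age bands are filled by age alone and sex is neither balanced nor named in the analysis, so band differences may partly reflect sex

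*Combined protocol and SAP*

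**What the plan says.** Under Number of Participants with Rationale, the combined protocol and SAP states: "We plan to recruit 60 participants (20 participants of each age group"). The reason given is "to allow for a sufficient cohort size for statistical analysis". Statistical Considerations repeats the quota and defines the bands: "with 20 participants per age group (20-40a, 40-60a and > 65a"). Age is the only characteristic on which recruitment is controlled, and Study Design describes the study as open label and non-randomised.

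Endpoint(s) lists the age comparison as a secondary endpoint: "1st sub-aim: Comparison across the defined age groups". Objective(s) makes clear that this sub-aim concerns kidney function as measured by mpMRI.

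The analysis methods are "t-tests, ANOVA as well as correlation coefficients and a multivariable ANOVA test". No factors or covariates are listed for any of them. Sex is not mentioned as a variable anywhere in the document.

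Two exclusions under Inclusion- / Exclusion Criteria bear only on women who could be pregnant or breast-feeding: "Women who are pregnant or breast feeding" and "Intention to become pregnant during the course of the study and lack of safe contraception".

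**The concern.** The scientific question is ageing, and the age bands are the groups being compared. Each band's sex mix is left to whoever volunteers. If one band holds noticeably more men than another, any MRI parameter that differs by sex will differ between those bands with no effect of age. The same holds for creatinine. Unadjusted t-tests and a one-way ANOVA would attribute that difference to age.

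The multivariable ANOVA could separate the two effects, but nothing commits the sponsor to including sex. With 20 per band, later adjustment loses precision when the mix is uneven, and it can do little if a band is nearly all one sex. The reliable time to settle the mix is before enrolment.

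**Working it through.** **The plan's own figure.** 3 bands × 20 = 60, which agrees. No alpha, power, effect size or SD is given, so the 60 cannot be derived further.

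**Inputs from the document.** 20 per band, three bands, age-only quota, non-randomised recruitment, no named covariates.

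**Assumptions (not in the document).** A 50:50 recruitment pool; a sex effect of 0.5 to 1.5 within-sex SD on a parameter; men's creatinine 10 to 20 µmol/l above women's; 5% to 30% of otherwise eligible young women excluded by the reproductive criteria.

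**1. Chance imbalance without a sex quota.** Let M1 and M2 be the numbers of men in two bands, each Binomial(20, 0.5). Then M1 + (20 − M2) is Binomial(40, 0.5), so

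P(|M1 − M2| ≥ 4) = 2 × P(Bin(40, 0.5) ≥ 24) = 0.268.

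That is about 13% in each direction. Summing the three-band probabilities over all combinations whose largest and smallest counts differ by at least 4 gives 0.509. For a gap of 8 or more, the figures are 0.017 for two given bands and 0.044 for some pair of the three.

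**2. What an imbalance does to a band contrast.** Bias = sex effect × (difference in number of women ÷ 20). The false-positive rates come from 40,000 simulated unadjusted two-sided 5% t-tests per setting, 20 v 20, with no age effect.

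| Women in the two bands | Bias (SD), sex effect 0.5 to 1.5 SD | False positives |
|---|---|---|
| 10 v 10 | 0 | 4.4% to 1.4% |
| 8 v 12 | 0.10 to 0.30 | 5.2% to 6.6% |
| 6 v 14 | 0.20 to 0.60 | 8.5% to 29.4% |

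For creatinine, a gap of 4 gives 0.20 × 10 to 0.20 × 20 = 2 to 4 µmol/l.

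For scale, the difference detectable with 80% power at 20 v 20 is √(2/20) × (1.960 + 0.842) ≈ 0.89 SD by the normal approximation, or 0.91 SD with the t distribution.

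In the 10 v 10 row the rate falls below 5% because sex differences stay in the error term of an unadjusted test. A quota without sex in the model would therefore remove the bias but leave the test conservative.

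**3. Contribution of the reproductive exclusions.** If a fraction x of young women is excluded from a 50:50 pool, the young band's female share is (1 − x)/(2 − x).

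| x | Female share | Women lost of 20 |
|---|---|---|
| 5% | 48.7% | 0.3 |
| 10% | 47.4% | 0.5 |
| 20% | 44.4% | 1.1 |
| 30% | 41.2% | 1.8 |

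The resulting shift is at most 0.0882 × 1.5 = 0.13 SD. For creatinine it runs from 0.0128 × 10 = 0.1 to 0.0882 × 20 = 1.8 µmol/l. With x = 20%, the probability that some pair of bands differs by 4 or more rises only from 0.509 to 0.536.

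**The case against.** A reader might infer that the pregnancy and contraception exclusions will make the youngest band mostly male. The document does not support that. The second criterion joins intention and lack of contraception with "and" in the plan's own text, so read literally it needs both and is narrow. The criteria can also reach some women in the 40-60 band. To reach 70% men by exclusion alone, (1 − x)/(2 − x) = 0.30 requires x = 57%; 75% men requires x = 67%. Nothing in the eligibility section suggests losses of that order. Nor is there support for saying that sex would hide or reverse an age trend, since no expected trend is stated.

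Three further arguments weaken the point. Chance imbalance is symmetric, and if the mix truly varied at random its effect would already be part of the sampling variation that a t-test or ANOVA allows for. The multivariable ANOVA might include sex. The study is exploratory, and the affected comparison is secondary.

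Much of this stands, and it keeps the point small. It does not remove it. Volunteers are not a random draw, so a random sex mix cannot be taken for granted. An imbalance that has occurred still biases that study's estimate. An adjustment that is merely possible is not planned.

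It is also fair that a sex quota does nothing about sex as a shared influence on the primary creatinine-MRI correlation. The point here is limited to the age-band comparison.

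**Conclusion.** The point holds as a cheap improvement. The documents establish that recruitment is controlled on age only, that allocation to bands is not random, and that sex is not named in any planned analysis. The supportable conclusion is that band differences may partly reflect sex, not that they are known to.

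A gap of 4 or more is quite likely (27% for two given bands, about 51% for some pair) but does limited harm to the error rate, with false positives at about 5% to 7%. A gap of 8 does real harm, up to about 29%, but is unlikely from a 50:50 pool (about 4% for some pair). The exclusions are a minor contributor. All sizes rest on the assumed pool, sex effects and exclusion rates, because the document gives none of these. The outcome that matters most for this sub-aim is the MRI parameters; the creatinine figures are only illustrative.

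**What to change.** Keep the total at 60 and make three changes:

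- Recruit 10 women and 10 men in each age band, closing each sex-by-band cell when it is full.
- Name sex as a factor in the age-band ANOVA and in the multivariable ANOVA.
- Report the number of women and men in each band.

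If the quota proves impracticable, the second and third changes still help. Under a model without a sex-by-age interaction, they remove the composition bias at some cost in precision.

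The cost is recruitment and analysis wording, slightly slower filling of the last cells, and one model degree of freedom (residual 60 − 3 = 57 becomes 60 − 4 = 56). No participants, visits or tests are added.

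### The renal exclusion contradicts itself and names creatinine as its only indicator, and no rule covers a kidney abnormality seen on the study scan

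*Combined protocol and SAP*

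**What the plan says.** All places are in the combined protocol and SAP.

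- **Inclusion- / Exclusion Criteria.** The renal item excludes "history of renal disease as indicated by a normal Quick-Serum-Creatinine level of less than 105" µmol/l. No urine test, eGFR limit, imaging criterion or record review is named as a further indicator of renal disease.
- **Background and Rationale.** Creatinine and eGFR "often remain within normal limits until significant nephron loss has occurred". The imaging markers are to be assessed for "differentiating physiological aging from early functional deterioration".
- **Study procedures.** Participants "undergo a multiparametric MRI examination prior to a capillary blood draw", unless a blood result less than a week old is on record. After that, "MRI parameters will then be examined by two readers and statistical analysis will be conducted". No eligibility check is placed between the scan and the analysis.
- **Ethical consideration.** "Incidental findings will be reported unless participants opt out beforehand".
- **Statistical Considerations.** Each of three age groups has 20 participants, and "All primary analyses will be performed with the full analysis set". That set is not defined anywhere.

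**The concern.** The study wants to describe how healthy kidneys change with age, so its conclusions depend on who counts as healthy. The one item that screens for renal disease is worded against its evident intent. Its only named indicator is a marker that the protocol itself describes as late.

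The study also obtains a kidney MRI on everyone. That scan may show a structural abnormality that creatinine misses, but the plan does not say what follows for the analysis.

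Structural disease may alter the MRI parameters while creatinine stays in range, and it is plausibly more common in the oldest group. Such participants could appear as discordant points in the primary correlation with creatinine and eGFR. They could also move the mean of the over-65 group, so that part of an apparent age effect would be disease. If handling is settled only after the data are seen, in an open-label study, the choice could be influenced by knowledge of age or creatinine.

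**Working it through.** **Step 1: what the exclusion item does under each reading.** Take three illustrative volunteers.

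| Volunteer | Literal wording (normal value marks disease) | Direction reversed, creatinine decides | History excludes on its own |
|---|---|---|---|
| No known disease, creatinine 85 µmol/l | excluded | admitted | admitted |
| Known polycystic kidneys, creatinine 85 µmol/l | excluded | **admitted** | excluded |
| No known disease, creatinine at or above 105 µmol/l | admitted | excluded | depends on whether creatinine is applied as well |

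The literal reading would turn away the people the study wants, so it cannot be meant. The other two readings disagree on the second volunteer, and the text does not choose between them.

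**Step 2: what happens after the scan.** Study procedures goes from the two readers to the statistics. Ethical consideration covers only whether the participant is told. Statistical Considerations names an analysis set without defining it. None of the three gives a rule for removing, flagging or separately analysing a participant with an abnormal kidney scan. Because the scan may precede the blood draw, creatinine eligibility itself may be known only after imaging, and this also has to be settled by the definition of the set.

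**Step 3: possible size.** The plan's own figure is 3 × 20 = 60, which agrees. It gives no alpha, power, effect size or SD, so there is no power calculation to reproduce. The inputs below, other than n = 20, are assumptions.

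Shift of a group mean = k × d / 20, where k is the number of affected participants in the group and d is their displacement in SD.

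- k = 1: 1 × 2 / 20 = 0.10 SD; 1 × 3 / 20 = 0.15 SD.
- k = 2: 2 × 2 / 20 = 0.20 SD; 2 × 3 / 20 = 0.30 SD.

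For comparison, the standard error of a group mean is 1 / √20 ≈ 0.22 SD.

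**Step 4: effect on a test of age.** This is a simulation with 20,000 runs, normal data with SD 1, 20 per group, no true age effect and two-sided alpha of 0.05 (assumed). Some of the over-65 group are displaced by d. The rejection rates for the youngest-versus-oldest t-test are:

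| d | 1 of 20 affected | 2 of 20 | 4 of 20 |
|---|---|---|---|
| 0.5 SD | 4.9% | 5.0% | 6.0% |
| 1 SD | 5.0% | 5.8% | 8.3% |
| 2 SD | 5.1% | 7.1% | 14.7% |

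The three-group ANOVA gives nearly the same rates. A displacement of 3 SD was not simulated. No figure is offered for the primary correlation, because the documents give nothing from which to derive one.

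**The case against.** Five points can fairly be made for the plan.

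1. **The item opens with history of renal disease, and the cohort is described as healthy.** A sensible site could exclude a volunteer with known polycystic kidneys or a nephrectomy on history alone. This stands as a possible reading. A reader might infer that known renal disease *will* be analysed as healthy ageing, but the documents do not support that. They leave the matter open.
2. **No text says that abnormal scans are kept.** A reader might infer retention from the use of the full analysis set. That set is undefined, so it shows neither retention nor removal. The sentence on incidental findings is a disclosure rule and is silent on analysis. What stands is that a rule is missing.
3. **Creatinine and the scan are not the only protections.** Hypertension is a separate exclusion, and the site consults medical records at least for a recent blood result. This is true, but neither is stated as a check for renal disease.
4. **The likely effect is small.** One case shifts a mean by less than its standard error, and one or two cases at 2 SD barely move the false-positive rate. This stands. It takes something like four of 20 at 2 SD to raise that rate to about 15%, and the study is exploratory.
5. **Removing and replacing participants because of their scan would select the cohort on the test under evaluation.** It might remove more older participants and leave an unusually clean oldest group. This stands, and it is why the fix keeps flagged participants in the primary analysis.

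**Conclusion.** The point holds as a defect of wording and pre-specification. The renal item contradicts itself and can be applied in ways that admit different people. Creatinine is its only named indicator, against the protocol's own account of creatinine's limits. The handling of kidney abnormalities on the study scan is unstated.

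It does not show that diseased participants will be enrolled or retained, and it does not show a bias of known size. The 0.10 to 0.15 SD (one case) and 0.20 to 0.30 SD (two cases) rest on an assumed displacement of 2 to 3 SD and on 20 per group. The documents give neither the number of cases nor the displacement. With so few cases the main loss is in interpretation: an age difference could not be cleanly attributed to ageing. The change is worth making because it is cheap and is credible only if made before the data are seen.

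**What to change.** 1. **Exclusion criteria.** Split the renal item in two: a known history of renal disease, irrespective of creatinine, and a separate creatinine item. The sponsor should reconcile the direction of the creatinine item with its evident intent.
2. **Analysis set.** Define the full analysis set, including how a participant is treated whose creatinine becomes known only after the scan.
3. **Scan review.** Add to Study procedures that the two existing readers, masked to creatinine and age group, flag structural kidney abnormalities from a list fixed in advance. State that this applies whether or not the participant opted out of disclosure, because the flag serves the analysis only.
4. **Analysis.** Keep all eligible participants in the primary analysis. Pre-specify a sensitivity analysis without flagged participants, and report the number flagged per age group.

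The cost is protocol wording, one medical-history question, a brief extra read of images already acquired, and one more analysis. Masking to age may be imperfect, since images can hint at it. The fixed list limits the room for judgement.
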